4.5.2.1. Disease-Related Events (not classified as AEs)

Disease-related events will be summarised by treatment group by overall frequency.

4.5.3. Laboratory Data

Summaries by shift tables of worst-case grade increase from baseline grade will be provided for all the lab tests that are gradable by DAIDS 2017 v2.1. These summaries will display the number and percentage of participants with a maximum post-baseline grade increasing from their baseline grade. Any increase in grade from baseline will be summarized along with any increase to a maximum grade of 2, any increase to a maximum grade of 3 and any increase to a maximum grade of 4. Missing baseline grade will be assumed as grade 0.

For laboratory tests with both low and high graded values, summaries will be provided separately and labelled by direction, e.g., sodium will be summarized as hyponatremia and hypernatremia separately.

Any clinically abnormal laboratory results which are not identified as AEs will be summarised separately, identification of such values will be described in the OPS document.

For lab tests that are not gradable by DAIDS 2017 v2.1, summaries of worst-case changes from baseline with respect to normal range will be generated. Decreases to low, changes to normal or no changes from baseline, and increases to high will be summarized for the worst-case post-baseline. If a participant has a decrease to low and an increase to high during the same time interval, then the participant is counted in both the “Decrease to Low” categories and the “Increase to High” categories.

Summaries and listings for hematology, and chemistry laboratory tests will be produced separately. Liver function laboratory tests will be included with chemistry lab tests.

Separate summary of hepatobiliary laboratory events (if any) including possible Hy’s law cases will be provided in addition to what has been described above.

Possible Hy’s law cases are defined as elevated alanine aminotransferase (ALT) $> 3 \times$ upper limit of normal (ULN), total bilirubin $\geq 2 \times$ ULN or international normalized ratio (INR) > 1.5 . Total bilirubin $\geq 2 \times$ ULN can be within 29 days following the ALT elevation and if direct bilirubin is available on the same day, it must be $\geq 35\%$ of total bilirubin.

The summary will be produced for worst case post baseline only. A plot for maximum post-baseline Total Bilirubin against ALT will also be produced.

4.5.4. Vital Signs

Summaries of grade increase in systolic blood pressure (SBP) and diastolic blood pressure (DBP) will be provided separately. These summaries will display the number and percentage of participants with any grade increase, increase to Grade 2 and increase to Grade 3 for worst case post-baseline only. The grade definition for SBP is: Grade 0 (<120), Grade 1 (120-139), Grade 2 (140-159), Grade 3 (≥ 160). The grade definition for DBP is: Grade 0 (<80), Grade 1 (80-89), Grade 2 (90-99), Grade 3 (≥ 100). The summaries will be produced for worst case post baseline only.

In addition, summaries of respiratory rate, heart rate and temperature will be provided.

A boxplot will be presented for blood pressures by treatment. A summary of temperature will also be presented by planned visit/timepoints and pre-defined categories i.e., $<38^{\circ}\text{C}$, $38^{\circ}\text{C}-<38.4^{\circ}\text{C}$, $38.4^{\circ}\text{C}-<38.9^{\circ}\text{C}$, $38.9^{\circ}\text{C}-<40^{\circ}\text{C}$ and $\geq 40^{\circ}\text{C}$.

In addition, listings of vital signs parameters (blood pressure, respiratory rate, heart rate and temperature) by visit will be provided.

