### 8.3.2. Vital Signs

On Day 1, vital signs should be recorded prior to dose administration and at 15 mins, 30 mins, 45 mins, 1 hour and 2 hours after infusion for participants who are part of the lead in, and for 15 mins, 30 mins, 45 mins and 1 hour after infusion for participants who are not part of the lead in.

- Vital sign measurements will include blood pressure, pulse rate, temperature (oral preferred), respiratory rate, and oxygen saturation.
- Blood pressure and pulse measurements will be assessed while participant is semi-supine or sitting with a completely automated device. Manual techniques will be used only if an automated device is not available.
- Blood pressure and pulse measurements should be preceded by at least 5 minutes of rest for the participant in a quiet setting without distractions (e.g., television, cell phones).

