4.5.2. Adverse Events

Adverse events analyses including the analysis of adverse events (AEs), Serious AEs (SAEs) and other significant AEs will be based on GSK Core Data Standards. As per the protocol, AEs are collected through Week 12 and SAEs collected through Week 36.

An overview summary of AEs will be produced, including counts and percentages of participants with:

- AEs
- AEs related to study intervention
- AEs leading to permanent discontinuation of study intervention,
- AEs leading to temporary interruption of study intervention
- Grade 3 and 4 AEs
- Grade 3 and 4 AEs related to study intervention,
- Grade 3 and 4 AEs leading to permanent discontinuation of study intervention,
- Grade 3 and 4 AEs leading to temporary interruption of study intervention
- SAEs
- SAEs related to study intervention,
- Fatal SAEs
- Fatal SAEs related to study intervention.
- Local infusion/injection site reactions

Adverse events will be coded using the latest version of the standard Medical Dictionary for Regulatory Affairs (MedDRA dictionary) and graded by the investigator according to the DAIDS 2017 v2.1.

The following adverse events will be considered of special interest (AESI) and will be summarised using frequency and percentages separately.

- Systemic infusion/injection related reactions (IRR) including hypersensitivity reactions (HSR); reactions within 24 hours of start of infusion will be identified using a list of MedDRA preferred terms confirmed by the Safety team.
- Local infusion/injection site reactions (ISR) will be identified using a list of MedDRA preferred terms confirmed by the Safety team.
- Immunogenicity (Anti-Drug Antibodies (ADA)) related adverse drug reactions will be reported. These potential events of ADAs will be detected by reviewing AEs that indicate HSR in those subjects who have positive anti-drug antibodies.
- Adverse events potentially related to antibody-dependent enhancement of disease (ADE) will be reported. These potential events of ADEs will be detected by reviewing adverse event/serious adverse events for an increase in the incidence and severity of COVID complications for a participant that cannot be explained by underlying risk factors.

In addition to the AE overview summary,

- Most common AEs defined as any AE preferred term (PT) with an incidence of at least $\geq 1\%$ (approx. 2 subjects) in any of the treatment group will be summarised using frequency and percentages separately.

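### The graded blood-pressure table counts only rises, so the SAP tabulates neither low readings nor falls after dosing

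*SAP*

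**What the plan says.** SAP 4.5.4 plans one graded blood-pressure analysis: "Summaries of grade increase in systolic blood pressure (SBP) and diastolic blood pressure (DBP) will be provided separately". The table shows participants with "any grade increase, increase to Grade 2 and increase to Grade 3 for worst case post-baseline only". The systolic cut-points read "The grade definition for SBP is: Grade 0 (<120), Grade 1 (120-139), Grade 2 (140-159", with Grade 3 from 160 upward. The diastolic ones read "The grade definition for DBP is: Grade 0 (<80), Grade 1 (80-89), Grade 2 (90-99", with Grade 3 from 100 upward. Neither scale has a grade for low values.

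Two other blood-pressure displays are planned in the same section:

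- "A boxplot will be presented for blood pressures by treatment", with no time point given;
- "listings of vital signs parameters (blood pressure, respiratory rate, heart rate and temperature) by visit will be provided".

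Numeric summaries are promised for respiratory rate, heart rate and temperature. Blood pressure is not in that list.

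SAP 4.5.2 makes "Systemic infusion/injection related reactions (IRR) including hypersensitivity reactions (HSR") an adverse event of special interest. SAP 1.2 has participants in the main study watched for 30 minutes after dosing, with vital signs every 15 minutes. In Amendment 4 of the protocol, which describes the substudy, section 8.3.2 states: "Vital sign measurements will include blood pressure, pulse rate, temperature (oral preferred), respiratory rate, and oxygen saturation". Section 2.3.1 of that amendment lists post-dose monitoring, vital signs included, among the mitigations for infusion and hypersensitivity reactions.

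**The concern.** The table looks in the direction that matters less for the risk these readings are meant to watch. Protocol 8.4.9.1 names anaphylaxis and acute anaphylactic shock among the relevant reactions. Protocol 2.3.1 reports one related anaphylaxis in a study of hospitalised participants and further post-marketing cases. In such reactions a fall in pressure is the sign of interest, and the plan's only blood-pressure table cannot show one.

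If falls were more frequent in one treatment group, no tabulated result would say so. A reader would have to find them in individual listings, or rely on investigators having reported them as events. Measured readings could provide a check on that reporting, which is useful in an open-label study, but the plan does not summarise them in a way that does so.

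**Working it through.** No sample-size, power or event figure is involved. The check applies the SAP 4.5.4 scale as written.

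**Inputs.** Cut-points 120, 140, 160 mmHg (systolic) and 80, 90, 100 mmHg (diastolic), from SAP 4.5.4.

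**Rule.** The grade g(v) is the number of cut-points at or below the reading v. The worst case is taken as the highest post-baseline grade. A participant is counted if that exceeds the baseline grade.

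**Illustrative profiles** (assumed readings, not from the documents):

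| Baseline | Post-dose readings | Systolic grade, baseline to worst | Diastolic grade, baseline to worst | Counted? |
|---|---|---|---|---|
| 118/76 | 70/40, then 118/76 | 0 to 0 | 0 to 0 | No |
| 135/85 | 70/40, then 130/82 | 1 to 1 | 1 to 1 | No |
| 150/95 | 75/45, then 148/92 | 2 to 2 | 2 to 2 | No |
| 165/102 | 70/40, then 150/95 | 3 to 2 | 3 to 2 | No |
| 118/76 | 121/78 | 0 to 1 | 0 to 0 | Yes (systolic) |
| 118/76 | 70/40, then 125/81 | 0 to 1 | 0 to 1 | Yes, but for the later rise |

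A systolic rise of 3 mmHg (118 to 121) is counted. A systolic fall of 48 mmHg (118 to 70) is not.

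**General result.** Because g(v) never decreases as v rises, a reading below baseline cannot have a higher grade than baseline. A grid in whole mmHg confirms this. For systolic baselines 60 to 220 with any lower value down to 40, and diastolic baselines 30 to 140 with any lower value down to 20, no fall counts as an increase. All systolic values from 40 to 119 and all diastolic values from 20 to 79 are Grade 0.

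**Does another section fill the gap?**

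- SAP 4.5.3 reports low and high laboratory values separately, and for tests without grades counts decreases to low as well as increases to high. It does not cover vital signs.
- SAP 6.2.5 has a counting rule for safety parameters with both high and low values. It relies on DAIDS or normal-range categories. SAP 4.5.4 gives blood pressure its own scale with no low category, and the grading table in 6.2.2 covers laboratory values only.
- SAP 4.5.5 summarises actual values and changes for oxygen saturation. Section 4.5.4 has no equivalent for blood pressure.

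**The case against.** The strongest reply is that detection of infusion reactions does not depend on this table. SAP 4.5.2 summarises reactions within 24 hours as events of special interest, along with Grade 3 and 4 events and events leading to interruption or discontinuation. SAP 4.5.1 counts infusions interrupted or stopped early. The Joint Safety Review Team reviews accumulating safety data. The boxplot could show a general downward shift, and the listings hold the recorded readings. Display details are left to the Output and Programming Specification, which is not among the documents.

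Most of this stands, and it limits the point to a missing summary. It does not close the gap. Event reporting depends on the investigator and on a preferred-term list that the SAP does not give. The boxplot and listings apply no criterion for a low value or a fall and yield no count. Under SAP 6.2.5 the latest of duplicate vital-sign records at a time point is used for summaries, so a low reading rechecked after recovery and entered at the same time point could be left to the listings alone. The programming specification might add a display, but the rule that the SAP states is increase only.

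Three stronger readings are tempting, and the documents do not support them:

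- A reader might infer that a fall would be presented as an improvement. The table has no improvement column; a fall is simply not counted.
- A reader might infer that the gap extends to the 2000 mg and up to 3000 mg cohorts. This SAP is version 2.0, based on Amendment 3, and covers the intramuscular versus intravenous comparison. Protocol 9.4 leaves the substudy to a SAP to be finalised before Cohort A is formally reported, and that SAP is not available here.
- A reader might want a number of participants missed. No rate of hypotension is given. The infusion-reaction terms that Protocol 2.3.1 lists for COMET-ICE do not name it, and any assumed rate would have no source in the documents.

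**Conclusion.** The point holds as a gap in one safety display. Under SAP 4.5.4 no fall in blood pressure, of any size, can be tabulated as worsening, and no other planned display counts low values or falls from pre-dose. This follows from the cut-points and the increase-only rule. It assumes only that worst case means the highest post-baseline grade, which is the natural reading of a table of grade increases.

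The consequence is modest. Low readings remain in the listings, generally in the boxplot, and in event reporting where investigators record them. The primary efficacy comparison is untouched. The number of participants concerned cannot be derived from the documents. The change is still worth making, because the stated rule points away from the direction relevant to the reactions the documents name, and it needs only data already collected.

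**What to change.** In SAP 4.5.4, summarise blood pressure in both directions, as 4.5.3 does for laboratory tests:

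- Label the existing table 'increase only'.
- Add a table by treatment group with the lowest post-dose systolic and diastolic values, the largest fall from the pre-dose value, and counts in low categories that the sponsor selects and states in the SAP. No cut-off is proposed here.
- Base it on the 15- and 30-minute readings of the main study, and say which record is used when a time point has more than one, given the latest-record rule in 6.2.5.
- Amendment 4 of the protocol already reports Day 29 results, so mark the table post hoc if it is added after that reporting.

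If the substudy SAP reuses this scale, make the same change there by cohort, at the 15, 30 and 45 minute and 1 hour readings and, for lead-in participants, the 2 hour reading.

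The cost is SAP wording and one extra table, with no new data collection. The downside is that some low readings of no clinical importance will be counted.

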4.5.5. Oxygen Saturation

Summaries of actual and changes in blood oxygen saturation (SpO₂) will be provided in addition a listing of participants administered oxygen.

Requirement for respiratory support is assessed according to the following categories:

1. Room air
2. Low flow nasal canulae/face mask
3. Non-re-breather mask or high flow nasal cannulae/ non-invasive ventilation (including continuous positive airway pressure support)
4. Mechanical ventilation / extra-corporeal membrane oxygenation
5. Other
6. Death

Changes in requirement for respiratory support (excluding room air) will be summarized using proportions of participants with change from baseline to higher respiratory support in each category by study day using a stacked bar chart.

4.6. Other Analyses

4.6.1. Subgroup analyses

The progression of COVID-19 through Day 29 will be summarised using counts and proportions for the following subgroups:

- Age (<65, \geq 65 years)
- BMI (<30, \geq 30kg/m²)
- Duration of symptoms (\leq 5, $>$ 5 days)
- Sex (Female, Male)

Change from baseline in viral load will be summarised by visit in the following subgroups:

- Age (<65, \geq 65 years)
- Baseline viral load (<4, \geq 4-<5, \geq 5-<6, \geq 6-<7, \geq 7 log₁₀ copies/mL)
- Duration of symptoms (\leq 5, $>$ 5 days)
- Serological status (Positive, Negative)

4.7. Interim Analyses

The Joint Safety Review Team (JSRT) comprising individuals from Vir and GSK will

review safety data at regular intervals throughout the conduct of the study. Details of the JSRT process is recorded in relevant SRT documents.

A single interim analysis (IA) was initially planned to be performed for evaluation of safety, efficacy and futility when approximately 50% of participants are enrolled and reach Day 29. The IA data was to be evaluated by an IDMC. However, prior to the time of the planned analysis, the JSRT noted a discrepancy in the rate of progression to hospitalization occurring in the 250mg IM arm compared with the 500mg IM and IV arms. Upon review of the cumulative data, the JSRT made the decision to pause enrollment into the 250mg IM arm on 04-August-2021 and escalated the issue to the IDMC. An ad hoc meeting of the IDMC was called on 11-August-2021 and based upon their review of the data, the IDMC concurred that enrollment in the 250mg IM arm should be discontinued. As this ad hoc IDMC meeting occurred prior to the timepoint when the formal interim analysis would have occurred and concluded with discontinuing one arm of the study combined with an unexpected rapid increase in the rate of enrollment, it was not feasible to conduct the formal interim analysis.

There will be 2 reporting efforts: the primary Day 29 efficacy and safety analyses, and the 36-Week Safety Follow-Up analyses.

4.8. Changes to Protocol Defined Analyses

Changes from the originally planned statistical analysis specified in the protocol are detailed in Table 2.

Table 2 Changes to Protocol Defined Analysis Plan

Protocol Defined Analysis	SAP Defined Analysis	Rationale for Changes

 Section 9.4.2: Planned primary endpoint model adjusted for treatment group, COVID-19 vaccination status, age (12-18, 19-64, ≥ 65 years old), region and gender. 	
 Planned primary endpoint model adjusted for treatment group, age (<65, ≥ 65 years old) and gender only. 	
 Model covariates amended due to small numbers of patients in non-US regions, small proportion of fully/partially vaccinated participants, and small number of participants <18 years.

5. SAMPLE SIZE DETERMINATION

Sotrovimab IM participants and sotrovimab IV participants were planned to be enrolled and randomized in a 1:1:1 ratio to receive a single dose IV infusion of sotrovimab or a single IM injection of sotrovimab at one of two dose levels, in an open-label manner.

Approximately 1020 (340 per arm) participants were planned to be randomly assigned to study intervention. This sample size will provide approximately 90% power to demonstrate that IM

injection of sotrovimab is non-inferior to IV infusion of sotrovimab in terms of the proportion of participants with progression of COVID-19 through Day 29 at the one-sided 2.5% significance level assuming COVID-19 progression rates of 2% in the sotrovimab IM and IV arms and 3.5% non-inferiority margin on the risk difference scale.

Following the discontinuation of sotrovimab 250 mg IM arm (See Section 4.7), no more participants were enrolled and randomized into this arm. The remaining participants were randomized in a 1:1 ratio to receive sotrovimab 500mg IV or sotrovimab 500 mg IM

Sample Size/Power Sensitivity

The table below shows power for showing non-inferiority for different true progression rates on the sotrovimab IV arm and when the progression rate in the sotrovimab 500mg IM arm is equal to or higher than that on IV, given a sample size of N=340 per arm.

		Progression rate in sotrovimab IV arm		
		1.0%	1.5%	2.0%
Progression rate in sotrovimab IM arm minus Progression rate in sotrovimab IV arm	0% (equal)	>99%	96%	90%
	+0.1%	99%	95%	88%
	+0.2%	98%	93%	85%
	+0.3%	97%	91%	82%

6. SUPPORTING DOCUMENTATION

6.1. Appendix 1 Study Population Analyses

The study population analyses will be based on the Intent-to-Treat Analysis Set, unless otherwise specified. Please see Section 3 of the SAP for more information on analysis sets.

6.1.1. Participant Disposition

A summary of subject status and subject disposition for the study conclusion record will be provided. This display will show the number and percentage of subjects who completed the study and who withdrew from the study, including primary and secondary reasons for study withdrawal and presented in the order they are displayed on the collection form. A subject is

considered to have completed the study if he/she has completed the Week 36 visit. The end of the study is defined as the date of the last contact of the last subject in the study.

A summary of the number and percentage of subjects who passed screening and entered the study or who failed screening and therefore were not entered into the study, will be summarized along with the reasons for failure will be summarized for those subjects who failed screening. This summary will be produced based on the Screened analysis set.

The number of subjects will be summarized by Country, Site Id. and Investigator Id. This summary will be produced based on the Enrolled analysis set

A summary of the duration in days in follow-up since infusion/injection will be summarized categorically for the Safety analysis set. The duration is calculated using the following formula:

$\min(\text{Date of study withdrawal, Date of Data Cut, Date of Study Completion}) - \text{Date of Dosing} + 1$

where the earlier date of either a subject withdrawal from the study, the current data cut date, or the date a subject completed the study are used. The summary will display duration overall and by mortality status: alive or deceased. The study withdrawal date for deceased subjects coincides with their death date. Duration categories post-dose include:

- Less than 5 days
- 5 to 10 days
- 11 to 14 days
- 15 to 29 days
- Greater than 29 days
- Greater than 85 days
- Greater than 141 days
- Greater than 169 days
- Greater than 224 days

A summary of treatment exposure will display the number of subjects exposed, the duration of treatment administration, and the number of subjects with infusion/injection interrupted or stopped early and not completed using the Safety set.

A summary of the number of subjects in each of the analysis sets described in the SAP Section 3 will be provided. Also, a listing will display subject exclusions from any analysis set using the Screened analysis set.

6.1.2. Demographic and Baseline Characteristics

The demographic characteristics (e.g., age including age categories, race, ethnicity, sex, baseline height, baseline BMI and its categories) will be summarized by descriptive statistics. An

additional summary of age ranges using the EMA clinical trial results disclosure requirement categories will be produced and is based on the Enrolled analysis set (see SAP section 3).

The high-level FDA race categories and detailed race subcategories collected on the CRF will be summarized along with categories for mixed race based on the Intent-to-treat analysis set.

Number of positive SARS-CoV-2 results, specimen type used for SARS-CoV-2 test, diagnostic method, risk factors for COVID-19 progression (as listed in the Protocol Inclusion Criteria), number of COVID-19 conditions met, types of symptoms present, and symptom duration will be summarized.

Additionally, the Baseline Disease Characteristics table will summarize subjects with a baseline obesity risk factor as (BMI $\geq 30\text{kg}/\text{m}^2$ for adult participants and BMI $\geq 85\text{th}$ percentile for age/gender based on CDC growth charts for adolescents) and summarize COPD risk factor to include the following protocol-defined conditions: history of chronic bronchitis, chronic obstructive lung disease, or emphysema with dyspnea on physical exertion.

The summary of stratification factors will be provided:

- Age: 12-17 years old, 18-64 years old, and ≥ 65 years old.
- COVID-19 Vaccination History: receipt of any COVID-19 vaccine.
- Region of the world (Europe, North America, South America, South Asia, Rest of Asia, Rest of the World).

Medical conditions collected at screening will be summarized separately by past and current. These factors will be summarized as collected for current medical conditions at screening.

